7.2 Demographic description and baseline description (FAS)

Table 7.2.1.1 Demographic description (FAS)

Item	Index	Total	Treatment group Control group
	N(Missing)		
Age (year)	Mean(SD)		
	Median		
	Q1,Q3		
	Min,Max		
	Statistics		
	P Value		
Sex	Male n(%)		
	Female n(%)		
	N (Missing)		
	Statistics		
	P value		
Marital status	Unmarried n(%)		
	Married n(%)		
	N (Missing)		
	Statistics		
	P value		
Body height (cm)	N(Missing)		
	Mean(SD)		
	Median		
	Q1,Q3		
	Min,Max		
	Statistics		
	P value		
Body weight (kg)	N(Missing)		
	Mean(SD)		
	Median		
	Q1,Q3		
	Min,Max		
	Statistics		
	P value		
BMI (Kg/m^2)	N(Missing)		
	Mean(SD)		
	Median		
	Q1,Q3		
	Min,Max		
	Statistics		

Item	Index	Total	Treatment group Control group
	P value		
Nationality	Han n(%)		
-	Others n(%)		
	N (Missing)		
	Statistics		
	P value		
Job category	Manual labor n(%))	
	Non-manual labor		
	n(%)		
	N (Missing)		
	Statistics		
	P value		

Table 7.2.1.2 Medical history (FAS)

Item	Index	Total	Treatment group Control group
	Cerebral infarction n(%)		
Diagnosed with	Acute phase n(%)		
Western medicine			
	N (Missing)		
	Statistics		
	P value		
	Atherothrombotic stroke n(%)	
TOAST type	Cardioembolism n(%)		
	Small artery occlusive stroke	n(%)	
	Ischemic stroke caused by oth	ner	
	reasons n(%)		
	Ischemic stroke of unknown	n causes	
	n(%)		
	N (Missing)		
	Statistics		
	P value		
	≤12h n(%)		
Course of disease	12-48h n(%)		
	48-72h n(%)		
	N (Missing)		
	Statistics		
	P value		
	First onset n(%)		
First onset	Recurrence n(%)		
/recurrence			
	N (Missing)		
	Statistics		
	P value		

Table 7.2.1.3 Past history (FAS)

Item	Index	Total	Treatment group Control group
Smoking history	With n(%)		
	Without n(%)		
	Quit smoking		
	N (Missing)		
	Statistics		
	P value		
History of alcohol	With n(%)		
intake			
	Without n(%)		
	n(%)		
	N (Missing)		
	Statistics		
	P value		
History of	Non-menopause n(%)		
menopause			
	Post-menopause n(%)		
	Not applicable n(%)		
	N (Missing)		
	Statistics		
	P value		
	With n(%)		
Drug allergy	Without n(%)		
history			
	N (Missing)		
	Statistics		
	P value		
	With n(%)		
Past history	Without n(%)		
	N (Missing)		
	Statistics		
	P value		

Table 7.2.1.4 Imaging examination (FAS)

Item	Index	Total	Treatment group Control group
	With n(%)		
Cerebral infarction	Without n(%)		
	N (Missing)		
	Statistics		
	P value		
	With n(%)		
Hemorrhagic	Without n(%)		
impression			
	N (Missing)		
	Statistics		
	P value		

Table 7.2.1.5 Therapeutic condition (FAS)

Item	Index	Total	Treatment group Control group
	With n(%)		
Drug for cerebral infarction	Without n(%)		
	N (Missing) Statistics P value		

Study No.: Document No.:

Item	Index	Total	Treatment group Control group
	With n(%)		
Thrombolytic therapy	Without n(%)		
	N (Missing)		
	Statistics		
	P value		
	With n(%)		
Have other disease	Without n(%)		
recently			
	N (Missing)		
	Statistics		
	P value		

Table 7.2.1.6 Drug combination (FAS)

Item	Index	Treatment group	Control group
	With n(%)		
New drug combination during study	Without n(%)		
	N (Missing)		
	Statistics		
	P value		

Table 7.2.1.7 Drug compliance (FAS)

Item	Index	Treatment group	Control group
	With n(%)		
Drug compliance conform to programme requirement	Without n(%)		
	N (Missing)		
	Statistics		
	P value		

7.3 Efficiency evaluation

7.3.1 Baseline effect indexes

Table 7.3.1.1 Baseline mRS score

		FAS	FAS		PPS	
		Treatment		Treatment	Control	
Item	Index	group	Control group	group	group	
Baseline NIHSS score	N(Missing)					
	Mean(SD)					
	Median					
	Q1,Q3					
	Min, Max					
	Statistics					
	P value					

Table 7.3.1.2 Baseline NIHSS score – as quantitative data

		FAS	PPS		
		Treatment		Treatment	
Item	Index	group	Control group	group	Control group
Baseline NIHSS score	N(Missing)				_
	Mean(SD)				

Study No.: Document No.:

			FAS		PPS	
		Treatment		Treatment		
Item	Index	group	Control group	group	Control group	
	Median				_	
	Q1,Q3					
	Min, Max					
	Statistics					
	P value					

Table 7.3.1.3 Baseline NIHSS score – as ranked data

		FAS		PPS	
		Treatment		Treatment	
Item	Index	group	Control group	group	Control group
Baseline NIHSS score	4-7 points n (%)				
	8-14 points n (%)				
	15-22 points n (%)				
	N (Missing)				
	Statistics				
	P value				

Table 7.3.1.4 Baseline BI score – as quantitative data

		FAS		PPS	_
		Treatment		Treatment	
Item	Index	group	Control group	group	Control group
	N(Missing)				_
Baseline BI score	Mean(SD)				
	Median				
	Q1,Q3				
	Min, Max				
	Statistics				
	P value				

Table 7.3.1.5 Baseline BI score – as enumeration data

		FAS		PPS	
		Treatment		Treatment	
Item	Index	group	Control group	group	Control group
Baseline BI score	<85 points n(%)				
	≥85 points n(%)				
	N (Missing)				
	Statistics				
	P value				
	P value				

7.3.2 Primary effect index - Improvement of daily life ability at 90 days after treatment Table 7.3.2.1 Improvement of daily life ability at 90 days after treatment

		FAS		PPS	
		Treatment		Treatment	_
Item	Index	group	Control group	group	Control group
	≤1 point n(%)				
mRS score at 90 days after	>1 point n(%)				
treatment					
	N (Missing)				
	Statistics				
	P value				
	Rate difference				
	95%CI				

Note: 1. Take CMH- χ^2 test to control central effect

2. Statistical description of baseline mRS score see Table 7.3.1.1

Table 7.3.2.2 Improvement of daily life ability at 90 days after treatment – take mRS=2 as limit

		FAS		PPS	
		Treatment		Treatment	_
Item	Index	group	Control group	group	Control group
	≤2 point n(%)				
mRS score at 90 days after	>2 point n(%)				
treatment					
	N (Missing)				
	Statistics				
	P value				
	95%CI				

Note: 1. Take CMH- χ^2 test to control central effect

2. Statistical description of baseline mRS score see Table 7.3.1.1

7.3.3 Secondary effect index - Improvement of neurological deficit

Table 7.3..3.1 Improvement of neurological deficits at 90 days after treatment

		FAS		PPS	
		Treatment		Treatment	
Item	Index	group	Control group	group	Control group
Improvement of neurological	Efficiency n(%)				
deficits at 90 days after	Inefficiency				
treatment	n(%)				
	Missing				
	Statistics				
	P value				

Note: It is effective for NIHSS score ≤ 1 or reducing 4 points or more

Table 7.3.3.2 Continuous change of NIHSS score at 90 days after treatment (FAS)

Item	Index	Treatment group	Control group	
	N(Missing)			
Baseline NIHSS score	Mean(SD)			
	Median			
	Q1,Q3			
	Min, Max			
	Statistics			
	P value			
	N(Missing)			
NIHSS score at 90 days after treatmen	t Mean(SD)			
	Median			
	Q1,Q3			
	Min, Max			
	Statistics			
	P value			
Change of NIHSS score at 90 days	N(Missing)			
after treatment comparing with that at baseline	Mean(SD)			
	Median			
	Q1,Q3			
	Min, Max			
	Statistics			
	P value			
	95%CI			
	Statistics			
	P value			

Table 7.3.3.3 Continuous change of NIHSS score at 90 days after treatment

The same as above

7.3.4 Secondary effect index - Improvement of daily life ability

Table 7.3.4.1 Inter-group comparison of improvement of daily life ability at 90 days after treatment

		FAS		PPS	
		Treatment		Treatment	
Item	Index	group	Control group	group	Control group
	With ability of				
	independent living				
	n(%)				
	Without ability of				
	independent living				
	n(%)				
Improvement of daily life	N (Missing)				
ability at 90 days after	ν υ,				
treatment					
	Statistics				
	P value				

Note: BI score≥85 points indicates the patient with ability of independent living

Table 7.3.4.2 Continuous change of BI score at 90 days after treatment (FAS)

7.4.2.2 The same as Table 7.4.2.2

Table 7.3.4.3 Continuous change of BI score at 90 days after treatment (PPS)

The same as above

7.3.5 Secondary effect index – disability rate

Table 7.3.5.1 Inter-group comparison of disability rate at 90 days after treatment

		FAS		PPS	
		Treatment		Treatment	
Item	Index	group	Control group	group	Control group
	Without self-care				
	ability n(%)				
Disability rate	With self-care				
	ability n(%)				
	N (Missing)				
	Statistics				
	P value				

Note: mRS≥3 indicates the patient without self-care ability

7.3.6 Secondary effect index – continuous change of mRS score

Table 7.3.6.1 Continuous change of mRS score (FAS)

Item	Index	Treatment group	Control group
	N(Missing)		
Baseline mRS score	Mean(SD)		
	Median		
	Q1,Q3		
	Min, Max		
	Statistics		
	P value		
	N(Missing)		
mRS score at 7 days after treatment	Mean(SD)		
•	Median		
	Q1,Q3		
	Min, Max		
	Statistics		
	P value		
	N(Missing)		
Change of mRS score at 7 days after treatment comparing with baseline	Mean(SD)		
r	Median		
	Q1,Q3		
	Min, Max		
	Statistics		
	P value		
	95%CI		
	Statistics		
	P value		
	N(Missing)		
mRS score at discharge day	Mean(SD)		
5	Median		
	Q1,Q3		
	Min, Max		
	Statistics		
	P值 P value		
	N(Missing)		
Comparison of mRS score at discharge			
day comparing with baseline	,		
	Median		
	Q1,Q3		
	Min, Max		
	Statistics		

Study No.: Document No.:

Item	Index	Treatment group	Control group
	P value		
	95%CI		
	P value		
	N(Missing)		
mRS score at 90 days after treatment	Mean(SD)		
	Median		
	Q1,Q3		
	Min, Max		
	Statistics		
	P value		
	N(Missing)		
Changes of mRS score at 90 days after	er Mean(SD)		
treatment comparing with baseline			
	Median		
	Q1,Q3		
	Min, Max		
	Statistics		
	P value		
	95%CI		
	Statistics		
	P value		

Table 7.3.6.2 Continuous change of mRS score (PPS)

The same as above

7.3.7 Secondary effect index – incidence of ischemic cerebrovascular diseases during follow-up period Table 7.3.7.1 Inter-group comparison of incidence of ischemic stroke within 90 days after treatment

		FAS		PPS	
		Treatment		Treatment	
Item	Index	group	Control group	group	Control group
	With n(%)				
	Without n(%)				
Have ischemic stroke within	N (Missing)				
90 days after treatment					
	Statistics				
	P value				

Table 7.3.7.2 Inter-group comparison of TIA incidence within 90 days after treatment

The same as above

Table 7.3.7.3 Inter-group comparison of ratio of new ischemic focus detected by MRI at last visit

		FAS		PPS	
		Treatment		Treatment	_
Item	Index	group	Control group	group	Control group
	With n(%)				_
	Without n(%)				
New ischemic focu	s detected N (Missing)				
by MRI at the last v	risit				
	Statistics				
	P value				

Table 7.3.7.4 Inter-group comparison of incidence of ischemic cerebrovascular disease during follow-up period

		FAS		PPS	
		Treatment		Treatment	
Item	Index	group	Control group	group	Control group
	With n(%)				
Have ischemic cerebrovascular disease during visit	Without n(%)				
	N (Missing)				
	Statistics				
	P value				

Note: Ischemic cerebrovascular diseases during follow-up period include: Ischemic stroke or TIA within 90 days after random treatment, or new ischemic focus detected by MRI at the last visit

7.3.8 Secondary effect index – incidence of combined vascular events during follow-up period Table 7.3.8.1 Inter-group comparison of incidence of ischemic stroke within 90 days after treatment The same as Table 7.3.7.1

Table 7.3.8.2 Inter-group comparison of incidence of myocardial infarction within 90 days after treatment. The same as above

Table 7.3.8.3 Inter-group comparison of incidence of vascular death within 90 days after treatment The same as above

Table 7.3.8.4 Inter-group comparison of incidence of vascular death during follow-up period

		FAS		PPS	
		Treatment		Treatment	
Item	Index	group	Control group	group	Control group
	With n(%)				
Combined vascular events	Without n(%)				
during follow-up period					
	N (Missing)				
	Statistics				
	P value				

Note: Definition of combined vascular events: Include any type of stroke (ischemic stroke and hemorrhagic stroke), TIA, myocardial infarction and vascular death.

7.4 Safety evaluation

7.4.1 Adverse event

Table 7.4.1.1 Inter-group comparison of incidence of adverse events

	Treatment group		Contro	ol group			
	Case	Case		Case	Case		
Item	times	number	Percentage	times	number	Percentage	P value
Adverse events							
Adverse events related to study drugs							
Serious adverse events							
Adverse events causing drop-out							
Severe adverse events							
Severe adverse events related to study							
drugs							

7.4.2 Physical examination

Table 7.4.2.1 Comparison of vital sign indexes between before and after treatment (SS) - systolic pressure (mmHg)

Item	Index	Treatment group	Control group
	N(Missing)		-
Systolic pressure at baseline (mmHg)	Mean(SD)		
	Median		
	Q1,Q3		
	Min, Max		
	Statistics		
	P value		
	N(Missing)		
Systolic pressure at 90 days after treatment (mmHg)	Mean(SD)		
E ,	Median		
	Q1,Q3		
	Min, Max		
	Statistics		
	P value		
	N(Missing)		
Changes of systolic pressure at 90 day			
after treatment comparing with that at			
baseline			
	Median		
	Q1,Q3		
	Min,Max		
	Statistics		
	P value		
	95%CI		
	Statistics		
	P value		

 $Table \ 7.4.2.2 \ Comparison \ of \ vital \ sign \ indexes \ between \ before \ and \ after \ treatment \ (SS) \ - \ diastolic \ pressure \ (mmHg)$

Table 7.4.2.3 Comparison of vital sign indexes between before and after treatment (SS) – heart rate (times/minute)

The same as above

Table 7.4.2.4 Comparison of vital sign indexes between before and after treatment (SS) – pulse (times/minute)

The same as above

Table 7.4.2.5 Comparison of vital sign indexes between before and after treatment (SS) – body temperature ($^{\circ}$ C)

The same as above

Table 7.4.2.6 Numbers and percentages of normal cases before physical examination and abnormal cases after physical examination (SS)

	Treatment group	Control group	
Item	Case number Percentage	Case number Percentage	P value
General condition			
Skin and superficial lymph nodes			
Head and neck			
Heart			
Lung			
Abdomen			
Nervous system			
Urogenital system			
Spine and four limbs			
Others			

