5.1. Inclusion criteria

- 1. Ischemic stroke within 72 h after onset, confirmed by MRI or CT;
- 2. Age 35–75 years, inclusive;
- 3. Patients with the first attack or patients with stroke history (modified Rankin Scale score 0-1);
- 4. Clear signs of localization of nervous system, NIHSS score 4 to 22;
- 5. Patient or proxy has signed *Informed Consent Form*.

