8.2 Visit 2 (V2, 7d)

- Record adverse events
- Record concomitant medications
- Physical examination
- Perform scale assessment (NIHSS, mRS, BI Index)
- Record combined vascular events
- Advise the subjects of the next follow-up date and inform them not to take the drug on the day of the follow-up

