9.1.2.1 Assessment and Procedures for Combined Vascular Events

After the occurrence of a combined vascular event, the study center must notify the sponsor within 24 hours upon receipt of the event notice. Vascular events will be reviewed by an independent Clinical Events Committee (CEC). Therefore, the endpoint event classification table will be included as part of the CRF. The investigator will record events in the aforementioned table and promptly submit supporting documents (admission and discharge records, medical records, death records, ECG, etc.). This information will be provided to the CEC for the determination of events.

The CEC is composed of a chairperson and 5–6 members. Each event will be independently reviewed by two members of the committee, and the conclusions will be submitted to the chairperson of the committee. If there is a disagreement between the two reviewing members or between the two reviewing members and the chairperson, when the number of dissenting events reaches a certain threshold, the entire committee will schedule a meeting to review the events.

9.2 Safety determination:

Adverse event assessment

• Clinical laboratory indicators:

Collect blood and urine samples in a fasting state (at least 10 hours of fasting, with water intake allowed but no consumption of coffee or tea) and send them to the laboratories of each center for testing according to uniform standards

Blood routine (hemoglobin, red blood cells, white blood cells, platelets), urine routine (urine protein, urine white blood cells, urine red blood cells), serum biochemistry (alanine aminotransferase, aspartate aminotransferase, alkaline phosphatase, total bilirubin, glutamine, urea nitrogen, creatinine, uric acid, blood glucose, total cholesterol, triglycerides, low-density lipoprotein, high-density lipoprotein), coagulation 4-item

12-lead ECG

Physical examination:

Comprehensive physical examination: General condition (including height, weight), vital signs (including blood pressure, pulse rate), skin (including hair and nails), eyes, ears, nose, and throat, neck/thyroid, chest/lungs, cardiovascular system, abdomen/gastrointestinal system, reproductive-urinary system (optional), nervous system, lymphatic system, and musculoskeletal system;

Simplified physical examination: General condition (including weight), vital signs (including blood pressure, pulse rate), chest/lungs, cardiovascular system

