4.5.1 Inclusion criteria

- 1. Have onset of ischemic stroke within 72 hours, and be diagnosed by CT/MRI;
- 2. At age of 35to 75;
- 3. First onset or with past history of ischemic stroke, but have recovered before this onset, that is with mRS score <1;
- 4. With clear nervous system orientation sign, and national institutes of health stroke scale (NIHSS) ≥4 and <22:
 - 5. The patient or his (her) legal representative has signed informed consent before the start of study.

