6.2.5 Safety analysis

Adverse events are described with case number, times and incidence of various adverse events, and $\chi 2$ test or Fisher's exact test is adopted for comparing the incidence between the two groups. At the same time, make a detailed list to describe the specific manifestation and extent of all adverse events and serious adverse events and their relation with drugs.

Statistically describe the vital signs at baseline and 90 days after treatment according to general principles, and make comparison between former and later times and inter-group comparison.

Make description of number of normal cases before treatment, number abnormal cases after treatment and their ratios in two groups, respectively, and $\chi 2$ test or Fisher's exact test is adopted for comparing the ratio between the two groups.

Make description of number of normal cases before treatment, number abnormal cases after treatment and their ratios in two groups, respectively, and $\chi 2$ test or Fisher's exact test is adopted for comparing the ratio between the two groups. Crosstab is adopted to describe the change of laboratory indexes before and after treatment for determining the clinical significance of these indexes.

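### The nervous-system row in the SAP's safety tables is empty for eligible patients, and no safety-set table counts neurological worsening from baseline

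*Combined protocol and SAP*

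**What the plan says.** SAP 7.4.2 contains "Table 7.4.2.6 Numbers and percentages of normal cases before physical examination and abnormal cases after physical examination (SS"). One of its ten rows is Nervous system, and each row carries a P value. The method is in SAP 6.2.5: "Make description of number of normal cases before treatment, number abnormal cases after treatment and their ratios in two groups, respectively", compared by chi-square or Fisher test.

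Eligibility fixes the baseline state. Protocol 5.1 requires "Clear signs of localization of nervous system, NIHSS score 4 to 22". SAP 4.5.1 requires "With clear nervous system orientation sign, and national institutes of health stroke scale (NIHSS) ≥4 and <22". The two differ at the upper limit, which does not matter here; the lower limit is the same.

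Before-and-after shift tables are planned, but not for physical examination: "Crosstab is adopted to describe the change of laboratory indexes before and after treatment". The shells in SAP 7.4.3 cover laboratory tests and ECG only.

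NIHSS is measured repeatedly. Protocol 8.2 (Day 7) asks sites to "Perform scale assessment (NIHSS, mRS, BI Index"), and 8.3 (discharge) and 8.4 (Day 90) do the same. In the SAP it is analysed as efficacy at Day 90: Table 7.3.3.1 classes each patient by the rule "It is effective for NIHSS score ≤ 1 or reducing 4 points or more", and Table 7.3.3.2 summarises change from baseline.

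**The concern.** A count of new abnormalities works only in patients who start out normal. For the nervous system in an acute stroke trial, eligibility removes all of them. The safety report would then show a zero row with nothing to test, and a reader could take it as evidence of no neurological harm.

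What is at stake is deterioration of the presenting deficit, especially early in treatment. If it is not judged a new stroke or TIA, no safety table counts it as such. It would reach the adverse-event totals only if a site reported it as an adverse event. The scores needed to count it are already collected at every scheduled follow-up visit.

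**Working it through.** **1. Arm size.** Protocol 4.2 and SAP 4.4 assume 40% versus 47%, two-sided alpha 0.05, power 80%, 1:1 allocation and a 20% dropout allowance. With pooled variance and no continuity correction:

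n = [1.96·√(2·0.435·0.565) + 0.8416·√(0.40·0.60 + 0.47·0.53)]² / 0.07² = 786.2, rounded up to 787 per arm.

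787 / (1 − 0.20) = 983.75, so 984 per arm and 1,968 in total. The plan's figures reproduce. They serve here only as the likely size of the safety set.

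**2. Who can enter the Nervous system row.** The risk set is the arm size times the share recorded as neurologically normal at baseline. If eligibility is met and correctly recorded, that is 984 × 0 = 0 per arm. The count is 0 versus 0 and no test is possible.

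**3. Allowing for recording errors (assumed shares, not in the documents).** Power is for 10% versus 15% becoming abnormal, also assumed, by a normal approximation that is rough at these sizes.

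| Share recorded normal | Risk set per arm (rounded down) | Power |
|---|---|---|
| 1% | 984 × 0.01 → 9 | about 5% |
| 2% | 984 × 0.02 → 19 | about 7% |
| 5% | 984 × 0.05 → 49 | about 11% |

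A non-zero row would therefore reflect deviations or errors and would still be uninformative.

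**4. Whether another table counts worsening.**

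| Place in SAP | What it gives | Counts patients who worsened neurologically? |
|---|---|---|
| Table 7.4.1.1 (safety) | Six aggregate adverse-event rows | No neurological row |
| 7.4.3 crosstabs (safety set) | Laboratory tests and ECG | No |
| Table 7.3.3.1 (FAS/PPS) | Effective or not, Day 90 | No; worsened and unchanged patients normally share the not-effective cell |
| Table 7.3.3.2 (FAS) | Mean, median, quartiles, range and CI of NIHSS change, Day 90 | No |
| Table 7.3.6.1 (FAS) | mRS change at Day 7, discharge and Day 90 | No; summary statistics only |
| Table 7.3.5.1 (FAS/PPS) | mRS of 3 or more, Day 90 | No; status, not change |
| 7.3.7 and 7.3.8 (FAS/PPS) | Ischemic stroke, TIA, new MRI lesions, combined vascular events | New events only |

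A small worsening group is hard to see in Table 7.3.3.2. If 8% versus 5% of patients (assumed) rose by exactly 4 points instead of staying unchanged, the mean would shift by (0.08 − 0.05) × 4 = 0.12 points. A group of 5% to 8% also lies beyond the upper quartile, so it could appear otherwise only through the maximum.

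**5. What a direct count would offer.** For the difference between two arms, each at an assumed 5%, the half-width is 1.96·√(2·0.05·0.95/n):

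- n = 984: 1.93 percentage points
- n = 787: 2.15 percentage points

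Two-sided power at 0.05, for 787 and 984 per arm, is 68% and 77% for 5% versus 8%, and 97% and 99% for 5% versus 10%. The documents give no worsening rates, so these are illustrations.

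**The case against.** The strongest reply is that neurological harm is compared elsewhere, and much of that stands. SAP 6.2.5 compares the incidence of various adverse events between arms. Protocol 10.1 defines an adverse event broadly and regardless of cause, and 10.4.2 keeps hemorrhagic stroke, all hemorrhagic events and all deaths as AE/SAE. Ischemic stroke and TIA are taken out of AE/SAE but have their own between-arm tables. Table 7.3.6.1 compares mRS change as early as Day 7, and the synopsis lists an ordinal mRS shift analysis. Protocol 8.6 requires a determination document, with neurological examination, within 72 hours of new neurological symptoms, and vascular events go to an independent committee.

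A reader might therefore go too far in inferring that the plan never compares neurological harm between arms. The documents do not support that. What they lack is narrower: the printed adverse-event shell has no neurological row, the stroke and mRS tables are efficacy analyses on FAS/PPS, and the documents collected under 8.6 feed no table of their own.

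Two other inferences also fail. One is that the nervous system might not be re-examined, because protocol 9.2 defines a simplified examination without it. No visit is assigned that examination, SAP 5.3 lists the nervous system within the physical examination, and NIHSS is scored at every scheduled follow-up visit. The other is that the Spine and four limbs row is nearly as empty. No figure supports this: protocol 9.2 lists nervous and musculoskeletal systems separately, and an NIHSS of 4 can come from non-limb items.

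**Conclusion.** The point holds in this limited form. The one nervous-system-specific row in the safety tables has a risk set of 0 of 984 per arm when patients are eligible and correctly recorded, and no safety-set table counts patients whose deficit worsened from baseline. The first statement follows from the wording of the table and the criteria and needs no assumed rate. The second rests on the table shells as printed; a by-term adverse-event table consistent with SAP 6.2.5 would narrow the gap but would still depend on site reporting.

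This is a gap in safety reporting. It should be closed before unblinding, but it changes neither the primary analysis nor the sample size.

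**What to change.** Replace the Nervous system row of Table 7.4.2.6 with the number and percentage of patients whose NIHSS rose by 4 or more points from baseline at Day 7, discharge and Day 90. Report it by arm in the safety set, with the rate difference and 95% CI. State the number assessed at each visit, and show deaths before the visit on a separate line so that they do not drop out of sight. Define the threshold in SAP 6.2.5.

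The cost is SAP wording and one extra table; no visit or data item is added. There are two limitations. The 4-point cut is borrowed, as the mirror of the plan's own improvement rule, and the documents do not justify it as a harm threshold. The discharge assessment also falls at a variable time, capped at Day 21, so Day 7 is the cleaner early comparison.
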